2.3. Secondary Objectives

To investigate the neuroplasticity in the brain through multiple neuro-imaging analysis (fMRI/MRI/DTI), with the goal to develop imaging biomarkers for image-guided neuro-rehabilitation framework so as to optimize early UL practice after stroke.

2.4. Potential Risks and benefits:

a. End Points - Efficacy

SURE program improves UL functional outcome and influences neuroplasticity positively to optimize UL recovery after stroke.

b. End Points - Safety

SURE Program

Subjects might experience fatigue at the early part of the exercise program.

The CPI will tailor and review subjects' exercises and the use of stroke-affected hand in daily tasks according subjects' stroke-affected hand's capability.

The CPI will consult the treating rehabilitation team (including doctors, therapists, nurses) on the subjects' medical and neurological stability before the commencement of teaching the exercises and each review.

First session of teaching exercises

CPI will pause, observe and ask each subject after teaching each exercise if they are tired. If they are tired, the CPI will stop teaching and let the subjects rest until they are not tired and ready to learn the next exercise. If the subjects are observed or express tiredness, the CPI will stop teaching the exercises for that session. Subjects will be advised to stop doing their exercises if they feel tired or rest until they feel ready to continue to do the exercises. The caregivers who are assisting the subjects with self-exercises will be given the similar advice. Subjects will also be asked to record any pain or fatigue that they experience during performance of self-exercises in their Exercise Log.

The next day after the first session

CPI will check the subjects' performance of their exercises and their level of tiredness, and also to reinforce the advice to rest if they are feeling tired.

Subsequent reviews

CPI will check the subjects' performance of their exercises and their level of tiredness, and also to reinforce the advice to rest if they are feeling tired.

Doctors, therapists and nurses who are taking care of the subjects in TTSRHC will be informed of the subjects' participation in SURE program and will be kindly requested to keep a look out of any verbal and non-verbal expressions of fatigue by the subjects. They will be informed to give similar advice by CPI to stop exercise and rest before continually or stop the exercises entirely if the subjects are too tired on that particular day. CPI will be informed by the treating team of their findings and will continue to monitor the subjects' suitability to continue with SURE program if there are reports of persistent fatigue due to self-exercises in the ward. Additional monitoring of fatigue level will be performed at pre, 2 weeks of intervention, post-intervention assessment using the Stanford Fatigue Scale.

A possible minimal risk is the development of allergy to the straps of the sensors. However, many research studies had used the sensors and there have been no reports of any adverse allergic reactions or problems reported with wearing the sensors.

Transcranial Magnetic Stimulation (TMS) Screening

TMS safety parameters have been documented and stimulation guidelines have been established (Wasserman, 1998). Seizures are the most important potential adverse event but are extremely rare. Mild headache, neck pain and discomfort from facial twitches are the most common and resolve spontaneously shortly after stimulation.

Exclusion criteria include pregnancy, presence of cardiac pacemakers, orthodontics (braces), metal implant and intracranial implants such as ventriculoperitoneal shunts and clips.

Functional Magnetic Resonance Imaging Investigation

Magnetic Resonance Imaging use radio waves similar to those used in radio and TV transmission. These have a much lower energy than X rays and are considered biologically safe. We follow strict safety guidelines which are designed to prevent the possible hazards of MRI: burns and electric shocks. The main risk in MRI is injury or death arising from the action of the strong magnetic field on any metal objects on or within the body. This may result in flying metal objects or damage to tissue. Strict screening procedures to remove external metal objects and exclude unsuitable volunteers will be carried out.

Exclusion criteria include prior history of central nervous system disorders, significant head trauma, structural brain lesions and psychiatric disturbance. In addition, subjects shall be excluded if they have pacemakers, metallic foreign bodies in the brain or eye, claustrophobia, tattoo, work with metal, or are pregnant.

Other potential issues include (i) Excessive heating of tissue due to absorption of RF energy, (ii) peripheral nerve stimulation (PNS) that may cause an uncomfortable but not harmful tingling sensation in the limbs and (iii) acoustic noise generated during the scanning. Excess power deposition will be avoided by hardware and software controls that limit this to well within FDA limits of 3.2W/kg, and the scanner has in-built warnings that let the operator know when a given sequence may cause PNS, so that he/she may adjust the sequence accordingly. Such accidents have never occurred at CIRC and have only very rarely occurred elsewhere in the world.

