5. STUDY DESIGN

Experimental procedure

The subjects will be randomly assigned to a control (N=10) and experimental group (N=10).

Experimental Group

The experimental group will receive one **SURE** program booklet with specific instructions and pictorial illustrations of each exercise and functional use according to their affected ULFM score. There are 3 booklets available (Level 1A for patients with affected ULFM score from 0 to 10; Level 1B for patients with affected

ULFM score from 11 to 22; Level 2 for patients with affected ULM score from 23 to 50). Each **SURE** program booklet consists of stretching exercises, strengthening exercises and performance of simple motor tasks such as reaching, picking up cubes etc. Each exercise will be graded and progressed according to the subjects' affected UL capability by the Clinical Principal Investigator (CPI) who is an experienced principal physiotherapist. The **SURE** program booklet also consists of selected motor tasks to be performed by the subjects using their affected UL. Functional activities such as subjects will be using their affected UL to wipe their faces; wiping the table after eating; applying lotion by the affected hand along the unaffected arm and legs after shower; drinking water from cup/ bottle; lifting and placing affected hand on table top; etc. Each functional motor task will be selected, graded and progressed by the PI according to the subjects' affected UL motor capability during the reviews. The subjects will be taught how to perform the exercises and functional tasks during the first session. The performance of the exercises and functional motor tasks will be reviewed by the CPI three times per week for the first 2 weeks, two times for the third week and one time for the fourth week of intervention period.

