The subjects will be asked to perform the exercises 60 minutes (3x 10- 20 minutes) distributed across morning, afternoon, and evening per day for 6 days per week during the 4-week intervention period. They will also be asked to perform the functional tasks as and when is required for their daily function for 6 days per week during the 4-week intervention period. The subjects will be given an Exercise Log to tick and track number of repetitions of the exercises and functional activities each day, the number of days the protocol is completed, and the level of fatigue and pain experienced. If the subject is discharged from the hospital before the 4 weeks of intervention period, he/ she has to carry on with the protocol till the intervention period ends. The CPI will continue to review exercises and the amount of affected UL use with the subjects at home if the subjects are discharged till the intervention period ends.

Control Group

The control group will receive an education booklet with 10 modules. The education booklet will contain information on stroke, recovery and management strategies after stroke. Subjects are to complete 2-3 modules per week and answer 1-2 simple questions after each module. Each module including answering questions takes approximately 5-10 minutes to complete. The CPI will review the information with the subjects 3 times per week for the first 2 weeks, two times for the third week and one time for the fourth week of intervention period.

Both groups will continue with their daily routine therapy sessions in the hospital. The treating therapists will record the duration of therapy of each subject per day.

UL functional outcome measures- ULM and ARAT will be assessed pre-intervention, 2 weeks after start of intervention, post-intervention, 1month and 3months post-intervention. Measures of **SURE** program's feasibility such as VAS pain score, fatigue level, and MAS of biceps and finger flexors will be measured pre-intervention, 2 weeks after start of intervention and post-intervention. A team member who is blinded to which group the subjects are in will perform the outcome measure assessments.

Multimodal imaging for the normal healthy control will be performed once to establish the activation pattern in normal. Multimodal imaging assessment for the patient subjects will be done pre-intervention, post-intervention, and 3months post-intervention.

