On the day of travel, the CPI will check with the treating doctor if the subject is clinical fit to travel, if the doctor deems the subject clinically unfit to travel, the ambulance services and TMS/ fMRI will be cancelled for that day and the subject will remain in the ward and not travel. If the doctor deems the subject clinically stable to travel, the subject will be accompanied by CPI and paramedic in the ambulance service to NUH and CIRC.

In the process of transportation, if the subject suffers any adverse events or re-stroke, the paramedic accompanying the subject in the ambulance will manage the emergency situations and send the subject to the nearest hospital Emergency Department. The CPI will call the treating doctor in TTSHRC to inform and update on the emergency situation and subject's location. The CPI will stay with the subject until further instructions has been given by the treating doctor in TTSHRC.

c. *Final Study Visit:*

The final study visit will be either the three-months post-intervention clinical assessment or fMRI investigation.

d. *Post Study Follow up and Procedures*

CPI will check on all clinical assessments and TPI will check on all fMRI investigations to ensure that all the assessments and investigations are done accurately and the results obtained are accurately. CPI and TPI will also check and monitor for any adverse events occurring during **SURE** program and fMRI investigations.

e. *Discontinuation Visit and Procedures*

All clinical assessments and fMRI investigations should be done until the subject indicate to the CPI that he/she want to withdraw voluntarily from participation in the study at any time. Subjects may also withdraw voluntarily from receiving the **SURE** program for any reason. All the withdrawals and reasons for withdrawal will be evaluated to gain an insight to the feasibility of SURE program. As **SURE** program is a safe exercise program, no efforts will be made to follow-up if the subject chooses to withdraw from the program, unless subject has specifically requested for follow-up.

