A one-way ANOVA test will be performed to assess differences across the visits (pre, post, and 3months post intervention). Provided a significant difference is found, a paired t-test will be used. Due to an abundance of measurable metabolites, metabolite analysis will be limited to those defined by our hypothesis (changes in GABA and Glx) to minimise multiple comparisons.

b. Safety Analysis

Safety analysis will be done by monitoring the adverse events and complaints of the study daily.

c. Interim Analysis

Interim analysis of the data and study's safety and complaints will be performed every quarterly. If the analysis of study's safety shows that the subjects' safety is compromised because of the study procedures, the study will stop.

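### Between scheduled assessments, fatigue and pain are actively solicited only in the SURE arm, so those reports have no like-for-like control count

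*Protocol*

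**What the plan says.** Three routes for picking up fatigue or pain between assessments are described for the SURE arm.

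- **Exercise Log.** Section 2.4b: "Subjects will also be asked to record any pain or fatigue that they experience during performance of self-exercises in their Exercise Log". Section 5, under Experimental Group, has the log track "the number of days the protocol is completed, and the level of fatigue and pain experienced".
- **CPI checks.** Section 2.4b has the CPI ask about tiredness while teaching the exercises. For the next day and for later reviews it states: "CPI will check the subjects' performance of their exercises and their level of tiredness".
- **Ward staff.** Section 2.4b says that doctors, therapists and nurses, once told of a subject's participation in SURE, "will be kindly requested to keep a look out of any verbal and non-verbal expressions of fatigue by the subjects", and the CPI is told what they find.

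For controls, Section 5 gives the same review timetable with different content: "The CPI will review the information with the subjects 3 times per week for the first 2 weeks", then twice in week 3 and once in week 4. The information meant is the education booklet. No log, symptom question or staff look-out is described.

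Two provisions are not limited by arm. Sections 9.4 and 11.2b provide daily review of adverse events. Sections 5 and 6 schedule fatigue, pain and spasticity scales at pre, 2 weeks and post, and Section 5 gives outcome assessment to a blinded team member. Section 6.3d is narrower: "CPI and TPI will also check and monitor for any adverse events occurring during" the SURE program and the fMRI investigations. The control program is not named.

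**The concern.** Fatigue and arm pain can occur after stroke whether or not a patient does extra exercise. If one arm is asked about them repeatedly and the other is not, more will be recorded in the first arm even when the true frequency is the same.

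This matters at two places. Section 6 judges the feasibility of SURE partly on the adverse events reported during the intervention period. Section 11.2c states: "If the analysis of study's safety shows that the subjects' safety is compromised because of the study procedures, the study will stop". Deciding that something happened because of a study procedure calls for some idea of how often it happens without that procedure. Fatigue is also central to the trial's rationale: Section 1.1 offers it as a possible reason why higher-intensity early practice did worse.

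A later analysis plan cannot repair the gap, because symptoms never asked about in controls cannot be recovered.

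**Working it through.** The protocol states no figure on this point. Section 11.1 justifies 10 per arm by feasibility, so there is no calculation to reproduce. The check is a count of the opportunities to report, followed by an illustration on assumed inputs.

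**Step 1: count from the documents**

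- Log days in SURE: 6 days per week × 4 weeks = 24.
- CPI reviews in each arm: 3 + 3 + 2 + 1 = 9.
- Scale readings after baseline: 2 (2 weeks and post), not limited by arm.

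| Route | SURE | Control |
|---|---|---|
| Daily log of pain and fatigue during self-exercise | up to 24 days | none described |
| CPI tiredness check | first session, next day, each later review | none described at the same 9 reviews |
| Ward-staff fatigue look-out | yes | none described |
| Fatigue and pain scales after baseline | 2 | 2 |
| General daily adverse-event review | yes | yes |

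The SURE-only routes are narrow. The log covers pain and fatigue; the CPI check and the staff look-out cover tiredness or fatigue only.

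**Step 2: does the general daily review close the gap?** Only in part. It applies to both arms, but the examples in Section 9.4 are medical events, strap allergy and fMRI events. The definitions in Section 9.1 list seizures during fMRI, MRI injury, burns or shocks, and strap allergy. Neither names fatigue or arm pain, and neither gives controls a question to answer.

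**Step 3: illustration (assumed inputs, not taken from the protocol).** Let the true proportion of subjects with a complaint be t in both arms, and let a complaint be recorded with probability d. The expected number recorded per arm is 10 × t × d. The chance of a spurious SURE excess is P(A − B ≥ 3), with A ~ Bin(10, t·d_SURE), B ~ Bin(10, t·d_control) and d_SURE = 0.9.

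| d_control | t | Expected recorded, SURE v control | P(SURE excess of 3 or more) |
|---|---|---|---|
| 0.9 | 30% / 50% / 70% | 2.7 v 2.7 / 4.5 v 4.5 / 6.3 v 6.3 | 10% / 13% / 12% |
| 0.6 | 30% / 50% / 70% | 2.7 v 1.8 / 4.5 v 3.0 / 6.3 v 4.2 | 19% / 32% / 43% |
| 0.3 | 30% / 50% / 70% | 2.7 v 0.9 / 4.5 v 1.5 / 6.3 v 2.1 | 33% / 61% / 80% |

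The true rates are equal throughout. The expected ratio is simply 0.9/0.6 = 1.5 or 0.9/0.3 = 3. The table shows how strongly the result depends on detection probabilities that the documents do not give.

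**The case against.** The strongest reply is that the SURE-only checks are tolerability management for an exercise that only one arm performs. The log asks about symptoms during self-exercise, which controls do not do, so that item cannot have a control counterpart. The protocol plans no between-arm count of log entries or staff reports; the stated test for pain, fatigue and spasticity in Section 11.2 compares pre with post. Section 9.1 does not list fatigue or exercise pain as adverse events, so it is an inference that such reports would reach the feasibility judgement or the safety review. The trial is a pilot of 10 per arm.

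Much of this stands, and it rules out three stronger readings that a reader might infer.

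- *Adverse events are sought only in SURE.* Sections 9.4 and 11.2b describe daily review without limit by arm.
- *Controls have no comparable fatigue or pain data.* The scheduled scales are not limited by arm and fall under blinded assessment, so they allow a like-for-like comparison at those visits.
- *Nearly all control symptoms will be missed, so SURE will look harmful.* One could argue that two readings over 24 program days cover 2/24 = 8% of days. That would require one-day symptoms, scales without recall beyond the day, full capture in SURE and no spontaneous reporting by controls. The documents support none of these.

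What the reply does not remove is the asymmetry itself. The nine control reviews already exist and are given no symptom question, and Section 6.3d words adverse-event monitoring around SURE and fMRI only.

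**Conclusion.** The point holds for fatigue and pain between scheduled assessments. By the routes described, SURE has up to 24 log days, CPI tiredness checks from the first session onward and a staff look-out; controls have none of these, despite the same nine reviews. Reports from these routes have no like-for-like control count and could be misread as caused by SURE when adverse events inform its feasibility (Section 6) or the study's safety (Section 11.2c). Any such bias would run against SURE.

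This is a risk, not a demonstrated bias, and its size cannot be derived from the documents; the table above only illustrates assumed detection rates. The conclusion also assumes that control reviews contain nothing beyond their stated content and that fatigue or pain reports would be considered among the adverse events. For a 10-versus-10 pilot this is an inexpensive improvement to make before data collection, not a flaw that undermines the trial.

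**What to change.** 1. **Section 5, Control Group (with a matching line under Experimental Group).** At each of the nine reviews the CPI asks the same fixed fatigue, arm-pain and adverse-event questions in both arms, on one form. After discharge, use the same mode of contact in both arms wherever a review takes place.
2. **Section 6.3d.** Reconcile it with Sections 9.4 and 11.2b so that adverse events are monitored during either program.
3. **Section 11.2.** Base between-arm comparison of fatigue and pain mainly on the blinded scheduled scores. Treat the common-form data as supportive, because Section 8.5 leaves the CPI aware of allocation. Report Exercise Log and ward-staff reports descriptively, as SURE-only tolerability data.

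The existing SURE tolerability checks stay unchanged.

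The cost is one short form and a few extra minutes per control review. While subjects are inpatients, this uses contacts already planned. After discharge the cost is less certain: Section 5 describes home review only under the experimental group, so matching the mode of contact may add some effort for controls.

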3. STUDY POPULATION

3.1. List the number of subjects to be enrolled.

20 subjects will be randomly assigned to a control (N=10) and experimental group (N=10). 4 normal healthy subjects will also be recruited for fMRI investigations.

3.2. Criteria for Recruitment

CPI will identify patients that will be admitted to TTSHRC based on their medical records. CPI will then approach the patients' therapist to confirm their eligibility for the recruitment to the study.

3.3. Inclusion Criteria

All patient subjects have to fit in the following Inclusion criteria to be included in the study: diagnosis of stroke due to infarct resulting in UL hemiparesis (with confirmation from MRI and Computed axial tomography (CT) scans); and admitted within first 21days post-stroke in TTSHRC with Montreal Cognitive Assessment (MoCA) score ≥ 19 . In addition, stroke subjects with positive motor evoked potential (MEP +ve) and with severe to moderate UL paresis (Upper Limb Fugl Meyer (ULFM) score below or equal to 50) admitted to TTSHRC will be selected. Subjects with severe and moderate UL paresis are selected because based on clinical observation subjects with this level severity require intensive UL practice to improve their UL functions, while subjects with mild paresis do not require such high intensity of UL practice for significant improvement. Investigation of motor evoked potential on extensor carpi radialis on the affected hand will be performed in NUH on stroke patients using a single Magstim 200 to prognosticate recovery. Subjects with MEP +ve will be selected to ensure that all the subjects chosen in this study have intact ipsilesional cortical spinal tract function to make comparison of UL recovery more consistent.

All normal healthy subjects aged 21 years old and above who are able to give informed consent and follow commands will be recruited.

3.4. Exclusion Criteria

All subjects (includes the normal healthy subjects and patient subjects) meeting any of the following exclusion criteria at baseline will be excluded from participation.

Exclusion criteria for subjects are:

1. recurrent stroke or previous history of brain injury
2. bilateral stroke
3. cardiac disease that limit function by exertional dyspnea, angina or severe fatigue
4. hemiplegic shoulder pain – visual analogue scale (VAS) $>5/10$
5. previous orthopaedic conditions on affected UL such as frozen shoulder and fracture that interfere

with affected UL movement

6. existing peripheral nerve or orthopaedic conditions that interfere with affected UL movement
7. severe aphasia, neglect, agitation, or depression that can limit participation
8. Additional exclusion criteria for TMS screening (Refer to Section 2.4b Endpoints Safety- TMS screening).
9. Additional exclusion criteria for fMRI investigations are inability to follow the fMRI instructions, claustrophobia, and MRI safety concerns (Refer to Section 2.4b Endpoints Safety- fMRI investigations).

